#### **Qualitative and interview Recruitment**

A convenience sample of participants in the intervention group will be recruited. Potential participants will be sent an invitation (Appendix D), via the post, to fill in the survey and/or participate in an interview with the researcher and assistant. A consent form (Appendix D) for participating in the interview is attached to the letter, while return of the completed survey will be

taken as consent to participate in the survey.

Follow up with the intervention participants will be made ten working days after the letter has been sent to determine if they are interested in participating.

**Note:** Nurses employed to work on the program will enrol and consent the patients. Nurses will be provided with training regarding informed consent from Assoc [name]. Consultant physicians will not be identifying, consenting or enrolling participants onto the study and hence any relationship of dependency issues would be mitigated.

**Participant recruitment:** (please see Appendix A for flow chart)

## **6. TREATMENT OF SUBJECTS**

At the patient's first appointment they will have the opportunity to discuss the information provided in the Participant Information and Consent Form (PICF) with the program staff. If the participant understands the information provided, is satisfied with the responses to any questions they have, and agree to participate they will be asked to provide informed consent by signing the PICF (please see appendix B for consent form). Patients unwilling to participate in the pilot or sign the consent form will not be enrolled and will not be contacted again.

### **Baseline Initial assessment and at 12 months - measures and observations**

Diabetes cohort

- Diabetes Type I or II
- HR, Rhythm
- Blood Pressure
- current HbA1c
- Serum Lipids
- Urine micro albumin
- Weight/height (BMI)
- Summary of health status including complications
- Medications including adjustment regime
- Validation/quality control of individual meter documented
- AQoL
- Health Education Impact Questionnaire
- Interview
- Survey

COPD cohort

- Recent lung function test
- HR, Rhythm
- Blood Pressure
- Weight/height (BMI)
- Barwon Health Respiratory Initial Health Assessment Tool
- 6 min walk test
- Mental health screen (K10)
- COPD Assessment Test (CAT)
- Summary of health status including complications

- Medications including adjustment regime
- AQoL
- Health Education Impact Questionnaire
- Interview
- Survey

## **7. GENERAL STUDY PROCEDURES**

### **The Pilot Study Service Model**

In summary the key aspects of the service model that differentiate it from current service provision includes;

- Personalised health care plans governed by consultants, with a 24-hour escalation process for signs and symptoms of deterioration.
- Tele-health monitoring component that enable virtual monitoring in the home. Enhancing self-care and increasing efficiency of home health services.
- Ability for early health care, nurse, allied health or medical assessment in the most appropriate place- home, clinic or rapid assessment unit as required in order to avoid hospital admission.

The model and infrastructure will permit the current gaps between acute responsiveness and community-based care to be addressed.

### **Staffing and Reporting**

For the pilot phase of the program the staffing model will consist of a Manager role .5 fte role. One full time equivalent (FTE) Clinical Nurse Specialist level with expertise in one or more of Endocrinology, Respiratory or Community based care provision and 2.8 equivalent full time (EFT) nursing staff for the 18 month of active program participation. Administration support will also be available 0.5 FTE.

The Manager will be responsible for overseeing the program, ensuring coordination of patient care, staff management, liaison with key stakeholders and progress monitoring of the program, including overseeing research processes and data collection.

Clinical Nurse Specialist will be employed for the initial 6 months of the program to to facilitate best practice approach to care planning and to facilitate the enrolment process of clients onto the program.

The equivalent of 2.8 full time staff will be responsible for the daily monitoring 7 days per week and direct care provision of the clients in the intervention group. This involves monitoring of the clients health via the information technology system, documenting daily care results in the Digital Medical Record, following up any variances to care plan parameters and consulting with the client as needed. Duties include liaising with the medical team and associated health professionals, such as Allied Health and Clinical Nurse Consultants and conducting home based visits as required.

Administration support will enable running of reports, ensure phone queries can be listed with clinical staff and to progress, support the enrolment process of clients, support the coordinated approach to enrolment of clients and to facilitate the replacement of equipment that is faulty as reported by participants.

As indicated above the BH Personalised Health Care Service team will organisationally report within the CH&RS service directorate and therefore access the standard CH&RS supervision framework

and undertake the directorate education and quality activities.

Data Collection Method for the post intervention evaluation will consist of a survey (Appendix G) made available for all study intervention participants. All patients will be mailed an invitation (Appendix F) to participate in the post intervention evaluation. Participants, regardless of their status within the program, eg. Completed, currently still receiving the intervention, or completed and still receiving the intervention will be offered the opportunity to respond about their experience by survey, the surveys will be returned to the Personalised Health Care mail box.

An invitation will also be extended to study intervention participants to participate in an interview. Invitations for this component of the evaluation will continue until n=12. The study population is seen as homogeneous in their experience. All are living with chronic conditions and all have received the same service intervention over the previous 12 months. It is expected that interviews with approximately 12 participants will produce saturation in response themes and provide evidence enough to produce the required result. Participants regardless of their status within the program, eg. Completed, currently still receiving the intervention, or completed and still receiving the intervention will be offered the opportunity to participate until n=12.

The interview will be conducted using the interview schedule (Appendix H). All interviews will be pre-booked with the patient and an assistant. The assistant will be a staff member from the Personalised Health Care team. The researcher will introduce themselves to the interviewee and will be present in the room to take field notes during the interview. The interview scheduled questions will be asked by the assistant. All interviews will be digitally recorded for verbatim transcription post the interview. Patients will be offered the option of having the interview undertaken using the facility of video conferencing that has been employed by the program or by arranging a time for the assistant and researcher to visit their home or other agreed meeting place.

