## Synopsis

### Study Rationale

### Personalised Health Care Proof of Concept Pilot Study

TITLE OF STUDY	Personalised Health Care Proof of Concept Pilot Study
PROTOCOL NUMBER	13/14
SPONSOR/FUNDING BODY	Victorian Department of Health \ Barwon Health
PROJECT PHASE/TYPE	Proof of concept pilot study
PRIMARY OBJECTIVE	To evaluate the effects of the personalised health care program, which includes care plans, escalation processes and tele-health.
CRITERIA FOR EVALUATION	

• ED admissions

• Acute Admissions

• LOS on acute admission

• Self-reported GP appointments

• To explore the patient experience of participation in a home tele-monitoring program that aims to support the self-management of their chronic disease.

• To understand the effects of a model of care on health literacy and self-management

• To understand the effect on various clinical measures

• To assess appropriate outcome measures for a fully powered randomised controlled trial

• To assess the variability of outcome measures to aid in sample size calculation for a fully powered randomised controlled trial

• Recruitment and retention rates

• Compliance with self-reporting

STUDY DESIGN	Randomised Control Methodology – proof of concept pilot study Post implementation 

• Qualitative interview using constant comparative

	
thematic analysis
 
 
• Survey
 

STUDY DURATION	
Screening: Rolling enrolment of 6 months On Study: 12 months

NUMBER OF PARTICIPANTS	
400 participants will be selected for the pilot study. This includes: 400 participants for the randomised pilot study Participants will be allocated to :
 
 
• 200 in the intervention ‘usual care plus Personalised Health Care’ group
 
• 200 in the control “usual care” group
 

NUMBER OF CENTRES	One

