### **Follow-up visit**

Within five working days the clients will receive a second home-based visit from one of the BH Personalised Health Care team members. At this visit the nurse will introduce and set up the information technology system demonstrating it to the client and providing education on the client's management plan.

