### **After hours Coverage and Escalation**

After hours are defined as after 5:00 pm and before 8:00am The only variance to the system between in hours and after hours is the staff will be the After Hours Community Nurse, and the escalation process for staff will be as per the McKellar After hours roster.

The service will be supported by a 24/24 on call system which during Monday-Friday 8am-5pm will be the BH Personalised Health Care team and after hours will be a rotating roster of on call PHC staff. Staff providing the after-hours support will be able to electronically access both the BH Personalised Health Care system and the BH Digital Medical Record to ensure care advice is appropriate and documented as per standard BH protocols. Training will be provided to the after Hours Community Nurse Coordinator and appropriate ED staff.

In line with other services within CH&RS the escalation process will be firstly to the Service Coordinator, then to the relevant expert consultant if the matter is clinical and unable to be resolved by staff, and finally to the Executive Director of CH&RS. If there is a system issue, that requires immediate attention, escalation will be directly to the Executive Director of CH&RS. The IT escalation protocol will be as per all current clinical Information Systems.

Escalation after-hours will be directed to the already existing McKellar After Hours Manager (who is based at the McKellar site) and then to the Director On- Call. Please refer to the flow chart attached in appendix C for more detail

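### Interviews on patient experience are conducted by a member of the service team being evaluated, while the researcher present only takes notes

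*Protocol*

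**What the plan says.** The Synopsis lists among the criteria for evaluation: "To explore the patient experience of participation in a home tele-monitoring program". The interview procedure is in Protocol Section 7, in the post-intervention evaluation text under Staffing and Reporting. It fixes three roles:

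- Who the assistant is: "The assistant will be a staff member from the Personalised Health Care team".
- Who conducts the interview: "The interview scheduled questions will be asked by the assistant".
- What the researcher does: "The researcher will introduce themselves to the interviewee and will be present in the room to take field notes during the interview".

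Invitations continue until 12 patients have been interviewed, whatever their status in the program: "Completed, currently still receiving the intervention, or completed and still receiving the intervention". Interviews are digitally recorded for verbatim transcription. They may be held by video link, at home or at another agreed place. A survey on the same experience is offered to all intervention participants.

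**The concern.** Patients are asked to judge a service by someone who belongs to it, and some still rely on it at the time. People in that position tend to soften or withhold criticism, so any distortion is likely to run one way, towards a favourable account. Analysis cannot recover a complaint that was never voiced. The interviews are meant to show how patients found the model of care, and they feed a listed evaluation criterion. Missing negative themes would make the model look more acceptable than it is when a larger trial is planned.

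**Working it through.** The point concerns who does what, so the check sets the relevant parts of the protocol side by side.

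**1. Is the assistant's team the one delivering the service?** Yes.
- Section 7, Staffing and Reporting, gives the program's nurses the daily monitoring and direct care of the intervention group.
- Section 8, Follow-up visit: "Within five working days the clients will receive a second home-based visit from one of the BH Personalised Health Care team members".
- Section 8, After hours Coverage and Escalation: "after hours will be a rotating roster of on call PHC staff".

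**2. Can the interviewee still depend on that team?** Yes. The eligible statuses include patients still receiving the intervention. The Exit Strategy in Section 8 adds that patients who remain unstable after 12 months continue to be monitored by the service.

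**3. Does any stated safeguard act when the answer is given?**

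| Safeguard | Where | What it does | Prevents withheld criticism? |
|---|---|---|---|
| Interview schedule | Section 7 | Standardises the questions | No |
| Recording and verbatim transcript | Section 7 | Preserves what was said | No |
| Pseudonyms, de-identification | Section 9, Confidentiality and Privacy | Protects the stored data | No: the team member asking still hears the answer |
| Two independent analysts | Section 10, Methods | Guards the coding of themes | No: acts afterwards |
| Consultants kept out of identification, consent and enrolment because of dependency | Section 5 | Covers physicians at recruitment | No: covers neither program staff nor interviews |

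The last row shows that the protocol recognises the dependency problem at recruitment but does not carry the principle through to the interview.

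**4. Can a size be given?** No. The protocol has no figure for how often criticism would be withheld and no rule for how many mentions make a theme. An illustration shows how far any figure would rest on assumptions. Take 12 interviews as independent draws, each with probability p that a given problem is voiced:

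- P(at least 2 mentions) = 1 − (1 − p)^12 − 12p(1 − p)^11
- P(at least 1 mention) = 1 − (1 − p)^12

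| Assumed p | At least 2 of 12 | At least 1 of 12 |
|---|---|---|
| 0.30 (nobody holds back) | 91.5% | 98.6% |
| 0.25 | 84.2% | not computed |
| 0.20 | 72.5% | not computed |
| 0.10 | 34.1% | 71.8% |

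All values of p are assumptions. With 30% as the true rate, the loss ranges from about 7 percentage points (91.5 − 84.2) to about 57 (91.5 − 34.1), depending on the assumed reticence. At p = 0.10 it falls to about 27 points (98.6 − 71.8) if one mention is enough. Independent draws are also doubtful, because Sections 3 and 5 specify a convenience sample.

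**The case against.** The strongest reply has four parts.

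- **There is another channel.** The survey goes to all intervention participants (at most 200), nobody asks its questions in person, and Confidentiality and Privacy calls it non-identified. This stands in part: a critical patient has a route that avoids face-to-face questioning, so the interviews are not the only source on experience. The route is imperfect, because surveys return to the Personalised Health Care mail box and carry the patient's age, gender and initial Health Education Impact Questionnaire results.
- **The interviewer may not be a familiar nurse.** The text says only that the assistant is a staff member, and the team includes a manager and administrative support. This stands: whether the patient knows the interviewer or depends on that person is unknown. The interviewer still belongs to the evaluated team.
- **The researcher may be no more independent.** The protocol does not place the researcher outside the service, and the program manager oversees research processes and data collection. This stands, and it makes the remedy conditional.
- **The reach is small.** About 12 interviews are involved, in a pilot without formal significance tests. This stands and limits the weight of the point. It does not justify leaving a cheap improvement undone.

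The interview schedule and invitation are appendices that are not shown, so any reassurance they offer patients cannot be judged.

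**Conclusion.** The concern holds as a weakness in a stated role allocation. It is neither a contradiction nor an omission. The service team conducts the interviews about its own service, including with patients still in its care, and no stated safeguard acts when the answer is given. The expected direction is favourable. This rests on the general tendency to hold back criticism from a care provider, not on data in the protocol.

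Three stronger readings are tempting, and the documents support none of them:

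- A reader might infer a large loss of negative themes, such as a fall from 91.5% to 34.1%. The arithmetic is right, but the rates and the two-mention threshold are assumed.
- A reader might infer that the whole conclusion on patient experience is unsound. That overlooks the survey and presumes that every interview is in fact distorted.
- A reader might infer that swapping the roles would remove the problem. A swap alone leaves the program staff member in the room, and its benefit depends on an independence that the protocol does not state.

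The randomised comparisons of emergency presentations, admissions and length of stay are untouched.

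**What to change.** In the post-intervention evaluation text of Section 7:

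1. Have the researcher ask the scheduled questions.
2. State that this researcher is not part of the team delivering care.
3. Limit the program-team assistant to booking and technical set-up, out of the room or off the video call while the questions are asked.

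The researcher already attends, so this adds no staff or visits. It costs some rapport and some field notes, and the digital recording largely makes up for the notes. If the researcher does belong to the service team, the swap gains little. The report should then say that the service's own team conducted the interviews, as a limitation on the findings about experience.

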## **8. EFFICACY EVALUATIONS**

### **Participant training and confirmation of care plan**

Following identification as per the research protocol, clients will be contacted by the program staff who will introduce the program and, as per the research protocol, enrol the client in one of the two cohorts through a randomisation process as described in the statistical analyses section.

### **Initial Visit**

Following agreement for enrolment and identification into the intervention group a staff member from the program will again contact the client the details of the persons care plan will be developed in consultation and authorised by the clients usual treating consultant \ GP. Prior to the commencement of the pilot study, all participants will be asked to complete Health Literacy and Self-Management questionnaires as well as at specific intervals over 12 months

### **Follow-up visit**

Within five working days the clients will receive a second home-based visit from one of the BH Personalised Health Care team members. At this visit the nurse will introduce and set up the information technology system demonstrating it to the client and providing education on the client's management plan.

### **Additional follow-up ( if required)**

The nurse will either call or visit (if participants are experiencing difficulties) for the following 2-3

days (or as client needs dictates) to assist the client in utilising the information technology system and re-enforce education of the clients care plan. Clients will be able to demonstrate full independent use of the system prior to nurse visits ceasing. The nurse will visit at any time throughout the pilot to address clinical care needs or reinforce information technology education if required. There are no limits set to prevent home-based follow-up.

### **Personalised Health Care Remote Patient Monitoring System**

The Remote Patient Monitoring (RPM) system used in this pilot project is a web based platform that can be accessed from any internet connected device. The patient, when accessing the platform, will be directed to their personalised care plan that has a questionnaire designed to educate and guide the client to monitor and support their own health. The peripheral devices that link to the system, enable the monitoring of clinical signs and symptoms such as SaO2, blood pressure and blood glucose measures.

For the health service clinicians accessing the platform, the RPM system identifies in real time which clients have recorded results at that point in time and which have not, it provides an indication of which results are at variance to the result parameters set for each individual, thus enabling a rapid and timely response.

The RPM system generates individualised reporting that allows the clinicians to monitor trends within a client's health care over time, enabling treatment to be appropriately adapted as and if required.

The client is required to log in to the system daily, to answer questions about their health and monitor aspects of their health. If clients do not complete their daily monitoring, the RPM system will alert the health service clinicians to this for follow up. The model is only as effective as the level of participation of the client, therefore for clients that are not willing or able to participate by choice or otherwise will need to be identified early, be removed or request to withdraw from the study.

Clients may choose to use their own web connected device to access the RPM system or alternatively Barwon Health will provide a suitable hardware device. If clients choose to use their own internet connected device, appropriate screening will be performed to ensure the device is suitable for purpose, including the quality of internet connectivity at the client's location. Client's using their own internet connection will be reimbursed at an appropriate rate for the amount of data transferred for the purpose of their RPM according to the data rates identified by the preferred vendor. If required Barwon Health will reimburse Internet costs or pay for new connections. If connectivity is not possible due to a patient's residential location, patient will be excluded from participation

Support for the RPM platform will be provided by the vendor and their associated affiliates depending on the client's support issue. Education for clients around use of the RPM device and platform will be provided by BH project staff in the set-up and establishment phase of the study. The vendor will provide the necessary education to BH staff to facilitate the resolution of most issues by the host site. In the event that the issue is beyond the scope and experience of the host site, the vendor or their affiliates will provide the required support. IT Support for the integration of the telehealth component will be provided by the host site's Information Technology Support Department (SWARH).

